12.11 Handling of Missing Data

Maximum likelihood, as used in MRMM, is a preferred method to address missing data considered at least missing at random (MAR). Depending upon the limited sample size, additional sensitivity analyses may be performed using LOCF or MI. As both MRMM and MI assume MAR data, the extent, pattern and reasons for missing data will be evaluated and described, if feasible. If necessary for the supportive analyses, MNAR can be evaluated using a pattern-mixture model (PMM), whenever possible.

13 DIRECT ACCESS TO SOURCE DATA/DOCUMENTS

The investigator/institution should permit study-related monitoring, audits, IEC review and regulatory inspections, and should provide direct access to the source data/medical record.

The monitor should verify that each subject has consented in writing to direct access to the original medical record/source data (by the use of written patient information and signed informed consent). During the monitoring, the data recorded in the eCRFs by the investigator will be checked for consistency with the source documents/medical record by the study monitor (source data verification). Any discrepancies of data should be documented and explained in the monitoring reports.

For each subject, the medical records should include the minimum following information:

- subject number and study ID
- date for information given, signing informed consent, completion of the ePHex study
- treatments given, including investigational product(s)
- visits to the clinic
- AE/SAE, if any
- concomitant medication
- time and reason for discontinuation, if any

There are data that are recorded only on the eCRF, which are associated with protocol-specific procedures and not with normal clinical care practice. For such clinical data the investigator would not be expected to duplicate the information. Source data location will then be specified in the Investigator file.

14 QUALITY CONTROL AND QUALITY ASSURANCE

14.1 Monitoring and Audits

Monitoring of the study will be arranged by the sponsor according to GCP guidelines. Monitoring visits will be performed regularly to the study sites during the study, to ensure that all aspects of the protocol are followed. Source documents will be reviewed for verification of consistency with data recorded on the Case Report Forms and product accountability will be performed as a part of the monitoring visits.

The study site may also be subject to quality assurance audits by the sponsor/CRO as well as inspection by the appropriate regulatory agencies.

It is important that the investigator and their relevant personnel are available during the monitoring visits and possible audits/inspections that study related records are made available, and that sufficient time is devoted to the monitoring process.

14.2 Site Personnel

Investigators and other key personnel shall provide curriculum vitae or equivalent, that will confirm their suitability for the clinical study. All investigators and key personnel should be listed together with their responsibilities in the study on a signature and delegation log.

It is the responsibility of the Investigator to ensure that all personnel involved in the study are fully informed of all relevant aspects of the study, including detailed knowledge of and training in all procedures to be followed.

15 ETHICS AND REGULATORY REQUIREMENTS

15.1 Ethics Review

It is the responsibility of the investigator to obtain written approval of the study protocol (incl. the patient information and informed consent) and subsequent protocol amendments from the IEC. The investigator should file all correspondence with the IEC, and a list of the IEC composition (names and position) should be filed in the Investigator File. A copy of the IEC approval should be forwarded to the sponsor.

15.2 Ethical Conduct of the Study

The study will be performed in accordance with the recommendations guiding physicians in biomedical research involving human patients adopted by the 18th World Medical Assembly, Helsinki, Finland, 1964 and later revisions and applicable ICH GCP guidelines.

The investigator is responsible for complying with all reporting procedures applicable to their IEC.

15.3 Written Informed Consent

It is the responsibility of the investigator to give each subject, prior to inclusion in the study, full and adequate verbal and written information regarding the purpose and procedures of the study and the possible risks involved. The patients must be informed about their right to withdraw from the study at any time, and that such withdrawal will not affect their future medical care, treatment or benefits to which the subject is otherwise entitled. The patients should be informed that the results will be stored and analysed in a computer, maintaining confidentiality in accordance with local data protection laws.

Furthermore, it is the responsibility of the investigator to obtain signed informed consent from all patients prior to initiation of any study-related activity. As the study involves children, age specific patient information sheets and parent information sheets should be prepared, and subject and/or parental consenting should depend on the age of the subject. The investigator or his/her designated representative, who gave the verbal and written information about the study to the subject, must also sign the informed consent form. A copy of the written patient information must be handed to each subject, to bring home. The investigator will confirm the receipt of informed consent from each subject by a recording in the eCRF. The signed ICFs should be filed by the Investigator in the Investigator File for possible future audits and inspections.

The investigator must always use the current IEC approved Patient Information/ICF and it must not be changed without prior discussion with the sponsor and approval from the IEC.

15.4 Regulatory Requirements

The study will be performed in compliance with national regulatory requirements. As with the IEC, clinical trial authorisation from the appropriate Regulatory Authority(ies) must be sought and obtained (as applicable to local country regulations), prior to the start of the study. The investigational product for this study will not be shipped to a study site until a copy of the applicable Regulatory Authority approval has been

received by the sponsor. In addition, the Regulatory Authority(ies) must approve amendments (as instructed by OxThera), receive SUSAR reports and annual safety updates or as required by local country regulations, and be notified of the end of the trial.

16 DATA HANDLING AND RECORDKEEPING

16.1 Case Report Forms

Study data for all subjects will be collected in a confidential fashion using an electronic Case Report Form (eCRF). All the information required by the protocol must be documented and any omissions explained. The investigator must review all eCRF entries for completeness and accuracy. Source documents, including all demographic and medical information, eCRFs and informed consent form for each subject in the study must be maintained by the Investigator. All information in the eCRFs must be traceable to the original source documents.

The eCRF must be signed and dated by the investigator who takes responsibility for the accuracy, completeness and legibility of the data reported to the sponsor in the eCRFs.

Concomitant medication, any medical history and Adverse Events will be coded using standardised medical dictionaries (medical dictionary for regulatory activities; MedDRA).

16.2 Retention of Records

All essential documents must be safely retained by the investigator for at least 2 years following the date a marketing application is approved for the drug, for the indication for which it is being investigated; or if no application is filed or if the application is not approved for such indication for 15 years after the investigation is discontinued and the regulatory authorities are notified.

16.3 Protection of Personal Data

The completion of the Study involves the collection and processing of Personal Data. All processing of Personal Data at the clinic and by the sponsor must be carried out in accordance with national legislation concerning the protection of Personal Data.

The investigator must ensure that the subject's privacy is maintained. On the eCRF or other documents submitted to OxThera, patients will be identified by a subject ID number only. Documents that are not submitted to OxThera (e.g., signed informed consent form) should be kept in a strictly confidential file by the investigator.

The investigator shall permit direct access to patients' records and source document for the purposes of monitoring, auditing, or inspection by OxThera, authorised representatives of OxThera, Regulatory Authorities and IECs.

As part of the required content of the informed consent, patients will be informed that their records may be reviewed by OxThera's designee and by regulatory agencies. Should access to medical record require a separate waiver or authorisation, it is the Investigator's responsibility to obtain such permission from the subject in writing before the subject is entered into the study.

17 FINANCING, INDEMNIFICATION AND INSURANCE

The Clinical Trial Agreement (CTA) outlines the compensation and payment terms of the study. The CTA must be signed before the start of the study. If there are differences between the CTA and the Protocol regarding certain rights and obligations the CTA is the prevailing document. Indemnification is covered by the CTA between the sponsor and the Institution.

OxThera has civil liability insurance, which covers this study in all participating countries.

18 CONFIDENTIALITY, INTELLECTUAL PROPERTY AND PUBLICATION POLICY

Investigator's, Institution's and OxThera IP AB's obligations regarding intellectual property, confidentiality and publication are described in detail in the Clinical Trial Agreement. They can be summarised as follows;

All information (whatever form) disclosed by OxThera to Institution, or generated pursuant to this study, shall be deemed to be confidential information. Except as required by applicable law, Institution shall not use or disclose to any party OxThera 's confidential information received pursuant to this study or otherwise, without the prior written consent of OxThera. All data generated or arising from the performance of the study shall be the exclusive property of OxThera.

It is intended to publish the results of the study as a whole once all patients have completed the study and the study has been analysed. If there is a publication, the Investigator that has the highest number of treated subjects will be the lead author, unless otherwise agreed. The investigator may not publish the results of their cohort of patients until the full study has been submitted for publication. The investigator may not submit for publication or present the results of this study without allowing OxThera 30 days in which to review and comment on the pre-publication manuscript. The investigator may not submit the results of the study for publication without the prior consent of OxThera, unless the review period has passed and there has been no reaction from the sponsor.

19 CHANGES TO THE STUDY PROTOCOL

The investigator should not implement any deviation from or changes to the protocol without agreement with the sponsor and prior review and documented approval from the IEC and Regulatory Authorities, except where necessary to eliminate an immediate hazard to the patients. All changes to the final study protocol must be documented in a written protocol amendment.

PP	Per protocol

PT	Preferred Term
Q1	The first quartile, being the 25th percentile of the data
Q3	The third quartile, being the 75th percentile of the data
QoL	Quality of Life
RTF	Rich Text Format
SAE	Serious Adverse Event
SAP	Statistical Analysis Plan
SAS	Statistical Analysis Software
SD	Standard Deviation
SE	Standard Error
SF36V2	36-Item Short Form Health Survey, version 2
SOC	System Organ Class
SDTM	Study Data Tabulation Model
STE	Speckle Tracking Echocardiography
TE	Traditional Echocardiography
TEAE	Treatment Emergent Adverse Event
UN	Unstructured
US	United States of America
VS	Vital signs
WBC	White Blood Cell
WHO	World Health Organization

1 GENERAL

This Statistical Analysis Plan (SAP) describes in detail the methods and presentation of the data analyses which will be conducted by AUTHOR! et al. / Certara for study OC5-OL-02. This plan is written in agreement with protocol version 2, dated 06 July 2020, annotated CRF version 6.0, dated 28 August 2020, the relevant GCP-ICH guidelines and sponsor requirements. Additional changes or updates of those documents or requirements may result in a new version of the statistical analysis plan.

A signed version of the SAP for study OC5-OL-02 is preferably to be finalized before database lock and unblinding of study OC5-DB-02.

2 STUDY INFORMATION

2.1 Study Objective(s)

The primary objective of this study is to evaluate the efficacy of Oxabact following two years continued treatment in subjects who have completed the Oxabact OC5-DB-02 study.

The secondary objective of this study is to obtain additional safety data from two years continued treatment with Oxabact.

2.2 Design of the Study

This study is a single arm, open label international multi-center study (OC5-OL-02, ePHex-OLE) to evaluate the efficacy and safety of Oxabact (OC5) treatment for an additional two years in subjects with Primary Hyperoxaluria (PH) who have previously been treated with Oxabact or placebo in the OC5-DB-02 (ePHex) study.

Henceforth in the document the OC5-DB-02 will be referred to as the ePHex study and the OC5-OL-02 will be referred to as the ePHex-OLE study.

2.3 Study medication

Subjects will receive open label OC5 (Oxabact) twice daily for 24 months.

2.4 Sample size

Approximately 16 subjects were anticipated to be included in the study, dependent on the number of subjects who complete ePHex and chose to participate in ePHex-OLE. It is anticipated, based on a drop-out rate of 25% per year, that there will be approximately 12 subjects completing the 12-month visit, and 9 subjects completing the 24-month visit.

Assuming a difference between treatment groups in eGFR change at month 24 from baseline of 5 mL/min/1.73 m² with an SD of 3, the power will be greater than 90% with a sample size of 16 subjects. This power calculation is done using a repeated measures model in a two-sided approach with $\alpha=5\%$, a 1:1 allocation ratio for a total of 16 subjects, and assuming a within subject correlation of 0,70.

At the time of signing off the Statistical Analysis Plan it is known that 18 subjects were included.

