The sample size is based on the number of subjects enrolled in the ongoing randomised, placebo-controlled double-blind ePHex study and who chose to participate in the ePHex-OLE study. The double-blind ePHex study plans to randomise approximately 22 subjects. It is anticipated that approximately 16 subjects will enter into the ePHex-OLE study and based on an anticipated 25% drop-out rate per year it is assumed that there will be approximately 12 patients completing the 12 month-visit, and 9 patients completing the 24 month-visit. Renal function in study subjects participating in the ePHex-OLE study will be analysed based on the randomised treatment assignment of subjects in the ePHex study using all data with a mixed effect repeated measures model (MRMM). Assuming a difference between treatment groups in eGFR change from baseline of 5 mL/min/1.73 m² with an SD of 3, the power will be greater than 90% with a sample size of 16 patients contributing with data.

Statistical Evaluation

The efficacy population (Full Analysis Set (FAS)) will include all subjects enrolled into the epHex-OLE study who receive at least one dose of open-label Oxabact treatment and have at least one efficacy assessment during the ePHex-OLE study. The safety population (Safety Analysis Set (SAF)) will include all subjects enrolled into the ePHex-OLE study who receive at least one dose of open-label Oxabact treatment.

Efficacy analyses, summaries and graphical presentations will include data from both the ePHex and ePHex-OLE studies based on the FAS, will be presented both for the overall population and according to the randomisation in the ePHex study. Safety summaries will include the safety data reported in the ePHex-OLE study and will be based on the SAF.

Baseline is defined as the baseline of the ePHex study. A second baseline will be calculated as the last measurement prior to open-label Oxabact treatment.

All data evaluations will be descriptive in nature due to the limited sample size. The primary analysis in the ePHex-OLE will be based on the 24-month data, with summaries and graphical presentations (patient profiles and spaghetti/scatter plots), while other time-points presented will be considered as supportive.

Statistical analyses, beyond summaries and graphical presentations of the data collected, will only be performed as supportive if there is sufficient sample size. No

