12.2 Sample Size Calculation

The sample size for this study is based on the number of subjects enrolled in the ongoing randomised, placebo-controlled double-blind ePHex study and who choose to participate in the ePHex-OLE study. The double-blind ePHex study plans to randomise approximately 22 subjects (11 subjects to Oxabact and 11 subjects to placebo). It is anticipated that approximately 18 subjects will complete the ePHex study, and approximately 16 subjects will enter into the ePHex-OLE study. Based on an anticipated 25% drop-out rate per year, it is assumed that there will be approximately 12 patients completing the 12-month-visit, and 9 patients completing the 24-month-visit. The observation period for the primary analyses of eGFR extends to 12 months in ePHex and 24 months in the ePHex-OLE study resulting in a maximum follow-up of 36 months for completers.

A supporting power analysis using a repeated measurements model in a two-sided approach with α =5%, a 1:1 allocation ratio and assuming a within patient correlation of 0,70, showed that a power greater than 90% is achieved if a difference between treatment groups of 5 ml/min/1.73 m² with a SD of 3 ml/min/1.73 m² is found. With a slightly lower difference of 4 mL/min/1.73 m² and a SD of 3 mL/min/1.73 m², or a difference of 5 mL/min/1.73 m² with a larger SD of 4 mL/min/1.73 m², the power is still above 80% (Table 11).

Table 11 Power Calculations

Standard deviation	Difference between treatment groups in eGFR (mL/min/1.73 m²)								
	3	3 4 5 6							
3	0,65635	0,88298	0,97601	0,99715					
4	0,42540	0,65635	0,83968	0,94338					
5	0,29375	0,47211	0,65635	0,80922					

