7.6 Statistical analysis primary and secondary endpoints

7.6.1 Primary endpoint

The primary efficacy endpoint is the change from baseline in kidney function (eGFR) after 12 and 24 months of open-label Oxabact treatment. The primary endpoint will be presented using the FAS population.

The primary analysis will be based on the 24-month data and using the baseline of the ePHex as primary baseline, while other time-points presented will be considered as supportive. A second analysis is done using the baseline of ePHex-OLE for the ePHex placebo subjects as baseline.

Change from baseline in kidney function (eGFR) will be calculated at each visit, using the two different baselines. Summary statistics of the measurements will be presented on a per-visit basis. Presentations will be per treatment group and overall.

To visualize the effects through time graphically, the following plots will be created:

- Individual plots will be created to visualize the course of eGFR values through time (including the ePHex values, as applicable). Both the actual values as well as change from baseline values will be presented.
- Mean \pm SE will be created to visualize the course of eGFR values through time (including the ePHex values, as applicable). Both the actual values as well as change from baseline values will be presented for the overall group and for both treatment groups, preferably in the same plot.
- Spaghetti plots per treatment group of the actual values will be created to visualize the group course of eGFR through time, using the same y-axis for visual comparison between groups. No spaghetti plots will be created for change from baseline. One plot will be created, using colors to discriminate both treatment groups (which combined will show the overall group).
- A plot presenting LS estimates \pm SE will be created, based on the mixed-effect repeated measures model stated below.

A statistical analysis will be performed using a mixed-effect repeated measures model (MRMM) on the change from baseline value at 12 and 24 months, with the following independent variables: treatment group, baseline eGFR value, time and time*treatment group interaction. If the assumption of normality is violated, a log transformation will be applied first (and a back transformation will be done on the results). SAS PROC MIXED (with the REML default) will be used for the analysis. The basic SAS code will be as follows.

```
proc mixed data=...;  
  class usubjid <time>;  

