  model change=treatment time treatment*time baseline;  
  repeated time / subject=usubjid(treatment) type=...;  
run;
```

The time variable will preferably be the same as used for ePHex, to be able to make comparisons.

Considering the variability of eGFR, an AR(1) covariance matrix will be used in the model, which assumes that a correlation between two consecutive measurements is higher than between two measurements further apart in time. If the model does not converge, an unstructured (UN) covariance matrix will be applied, to allow variances and covariance to differ at and between measurements. As the use of an unstructured (UN) covariance matrix requires estimation of a larger number of variance and covariance parameters (and is thus computationally more intense), the model is likely not converge if AR(1) already did not converge. If that occurs, the structure will be adapted to respectively Toeplitz or Compound Symmetry (CS).

From this model, the comparison at 12 and 24 months will be extracted (both overall as well as per treatment group). Comparisons of other visits will be extracted as well and presented as secondary. The tables will display the LS means, SE, 95% CI for each visit and the p-values for the differences at 12 and 24 months.

In addition, since the model provides a test of difference in slopes using the proposed time-by-treatment interaction, treatment slopes and slope differences on change will be presented as well. Only the values after first open label treatment will be used for determination of the slopes.

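### SAP 2.4 presents power above 90% as month-24 power, but the calculation behind it averages over visits with nobody lost; at month 24 with the plan's own drop-out, power is about 57–85%

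*SAP*

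**What the plan says.** SAP 2.4 bases its power statement on a month-24 effect, "Assuming a difference between treatment groups in eGFR change at month 24 from baseline", of 5 mL/min/1.73 m² with SD 3, and concludes that "the power will be greater than 90% with a sample size of 16 subjects". It describes the method as a two-sided 5% repeated measures calculation with 1:1 allocation and a within-subject correlation of 0.70. The paragraph just before it expects about 12 subjects at month 12 and 9 at month 24, from drop-out of 25% per year. The section also records that 18 subjects were in fact included.

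Protocol 12.2 reports the same calculation ("A supporting power analysis using a repeated measurements model in a two-sided approach") and gives the results in Table 11, where 5 with SD 3 has power 0.97601. It expects "approximately 12 patients completing the 12-month-visit, and 9 patients completing the 24-month-visit". It names no time point for the difference and does not give the number of repeated measurements. The protocol synopsis says that "the power will be greater than 90% with a sample size of 16 patients contributing with data", also without a time point. The month-24 label is therefore found only in the SAP.

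SAP 7.6.1 makes month 24 the main time point ("The primary analysis will be based on the 24-month data"). For the mixed model it says "From this model, the comparison at 12 and 24 months will be extracted", and its tables are to show "the p-values for the differences at 12 and 24 months".

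**The concern.** Power belongs to a particular contrast and a particular amount of data. SAP 2.4 names the month-24 difference, and SAP 7.6.1 reports that difference with its own p-value, so a reader will take the stated power as applying to it. A difference averaged over many visits has a smaller standard error than a difference at one visit. Month 24 is also the visit at which the plan expects the most subjects to have been lost. If Table 11 is a visit average in complete data, both features make the figure too favourable for the comparison it is attached to. A month-24 p-value above 0.05 could then be read as evidence against a difference of 5, when the comparison had much less chance of detecting one.

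**Working it through.** **Inputs.** Difference 5 and SD 3 (SAP 2.4; protocol 12.2); two-sided 5%; 8 + 8 subjects; correlation 0.70; 16 → 12 → 9 subjects at months 0, 12 and 24. The ePHex-OLE schedule has 10 visits after month 0. Neither document states the number of visits used in the power calculation or the visit count of ePHex.

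**Step 1: reproduce Table 11.** For a difference D averaged over m equally correlated visits, n = 8 per group:

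SE = SD × √[(2/8) × (0.70 + 0.30/m)], power = Φ(D/SE − 1.96).

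With m = 18, D = 5, SD = 3: 0.70 + 0.30/18 = 0.71667; SE = 3 × √0.17917 = 1.270; 5/1.270 − 1.96 = 1.978; Φ = 0.97601, as printed. The largest error over all 12 cells is:

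| m | Largest error |
|---|---|
| 1 | 0.14038 |
| 10 | 0.00800 |
| 17 | 0.00059 |
| 18 | 0.00000 |
| 19 | 0.00054 |

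No other variant tried (t reference, AR(1), other group sizes, change-score variances) matches at the printed precision. Table 11 is arithmetically right, but as a visit average in complete data.

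**Step 2: month 24 alone, nobody lost (m = 1).** SE = 3 × √(2/8) = 1.50; 5/1.50 − 1.96 = 1.373; Φ = 0.915. The t columns use the noncentral t with 14 df.

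| Difference / SD | Table 11 | Month 24, normal | Month 24, t |
|---|---|---|---|
| 5 / 3 | 97.6% | 91.5% | 87.2% |
| 4 / 3 | 88.3% | 76.0% | 69.9% |
| 5 / 4 | 84.0% | 70.5% | 64.3% |

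The last two rows matter only if the protocol's cases of power above 80% are read as month-24 power, which the protocol does not say.

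**Step 3: month 24 with the plan's drop-out, 5 / SD 3.**

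- *Completers only*, 9 subjects, assumed split 5/4: SE = 3 × √(1/5 + 1/4) = 2.012; 5/2.012 − 1.96 = 0.525; power 70.0% (normal) or 57.1% (t, 7 df).
- *Repeated measures model* using the earlier visits of those who leave: generalised least squares standard error for the month-24 difference, covariance treated as known, 12 subjects at month 12, drop-out placed early, midway or late, with the 10 extension visits alone or with 8 assumed ePHex visits added.

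| Covariance | SE (complete: 1.50) | Power, t with 7 df, to normal |
|---|---|---|
| AR(1), the SAP's first choice; 0.70 taken as adjacent-visit correlation | 1.88–2.00 | 57.7%–76.0% |
| Compound symmetry | 1.68–1.73 | 69.9%–84.5% |

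**Step 4: the 18 subjects now known.** Assuming 9/9 and nobody lost: 94.2% (normal) or 91.3% (t). At 25% per year, 18 × 0.75 × 0.75 ≈ 10 completers; split 5/5, power is 75.0% (normal) or 63.8% (t). The repeated measures model gives about 65–78% under AR(1) and 76–88% under compound symmetry.

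**Step 5: expected precision at month 24, SD 3.** 16 complete: 2.145 × 1.50 = 3.2. Nine completers: 2.365 × 2.012 = 4.8 (95% half-widths, mL/min/1.73 m²).

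**The case against.** The strongest reply is that the SAP sentence holds on its own terms. It says above 90% with 16 subjects, and a month-24 comparison in 16 observed subjects has 91.5% power by the plan's normal approximation; with 18 observed it exceeds 90% by either method. That stands: the time point alone does not break the claim. But it needs every subject to be present at month 24, and the preceding paragraph expects 9 of 16.

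The protocol also has a fair defence. It names no time point, the synopsis makes its figure conditional on 16 contributing patients, and drop-out hardly affects a visit average. With 16 → 12 → 9 subjects, 18 visits and compound symmetry, the SE for the average is about 1.27–1.28 and power stays above 95%. So the protocol's figure survives its own attrition as a visit average; what is missing there is a statement of what it is.

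The 57–85% range is wide and rests on assumptions. Its lower end is a completers-only t test, which is close in form to the month-24 ANCOVA in SAP 7.6.1 but is not the main model. No variant credits the baseline eGFR covariate. These points affect where in the range the truth lies; the most favourable variant tried still reaches only 84.5%, or about 88% with 18 enrolled.

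Finally, the study is descriptive, its size is fixed by roll-over, and SAP 7.1 calls any p-value indicative only. This limits the consequence but does not make the printed figure right for the contrast it names.

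**Conclusion.** The point holds. The power in SAP 2.4 belongs to a complete-data, visit-averaged difference, and the SAP labels it month 24. Changing the contrast alone takes 5 / SD 3 from 97.6% to 91.5% (normal) or 87.2% (t). The plan's own drop-out then takes it to about 57–85% with 16 enrolled, or about 64–88% with 18. This is a fault of labelling and of an unstated completeness assumption; Table 11 contains no calculation error.

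The conclusion does not depend on the inferred 18 visits, since a single-visit reading misses the table by up to 14 points. The drop-out ranges do depend on the assumed group splits, drop-out timing, degrees of freedom (7 up to the normal limit) and the reading of 0.70 under AR(1). No sample size or decision changes, but the statement should be corrected because month-24 p-values will be shown.

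**What to change.** In SAP 2.4, either remove the month-24 label from the present figure or say that it is power for the difference averaged over visits with complete data in 16 subjects, with the sponsor confirming the visit count (18 by inference). Beside it, give month-24 power under the planned drop-out as a range with its assumptions, preferably for the 18 subjects included.

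In protocol 12.2 and the synopsis, state the contrast, the number of visits and the complete-data assumption behind Table 11.

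Alternatively, delete the power claim, since no formal testing is planned, and give the expected month-24 95% confidence-interval half-width at SD 3: about 3.2 mL/min/1.73 m² with 16 complete and about 4.8 with 9 completers. This suits a descriptive study better.

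The cost is wording only, with a less favourable figure on the page. No patients, visits or analyses are added.
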